6.5. Rescue Visit, if applicable

Subjects who require rescue therapy per [Section 5.6](#) must have glycemic rescue therapy initiated at either a scheduled or unscheduled visit and not by a telephone call. The following procedures are to be completed at a rescue visit:

- Review and update concomitant medications since last visit,
- Assess treatment compliance with investigational product and counsel subjects who have been <80% compliant [refer to [Section 5.3.5](#)].
- Measure body weight in duplicate [refer to [Section 0](#)].
- Collect triplicate measurement of sitting blood pressure and pulse rate [refer to [Section 7.4.2](#)].
- Obtain duplicate orthostatic blood pressure and pulse rate measurement (supine \rightarrow standing) [refer to [Section 7.4.3](#)].
- Conduct brief physical examination which includes assessment of heart, lungs, abdomen and extremities.
- Obtain blood specimens for clinical laboratory tests [refer to [Section 7.4.1](#)] including chemistry, hematology, urinalysis, lipid panel, HbA1c (only if visit is at least 6 weeks after randomization) and FPG.

- Conduct inquiry about any spontaneously reported AEs by asking the subject to respond to a non-leading question such as “how do you feel?” Assess potential clinical events for adjudication [refer to [Section 7.6](#)].
- Review self-monitoring blood glucose and Hypoglycemia Assessment logs completed by the subject.
- Diet and exercise monitoring (see [Section 6.1.2](#)).
- Dispense glycemic rescue therapy with glimepiride. Dosing of open-label glimepiride is at the Investigator’s discretion.
- Provide subject with glucose meter supplies and additional self-monitoring blood glucose or hypoglycemia assessment logs, as needed.

6.6. Subject Withdrawal

Subjects may withdraw from the trial at any time at their own request, or they may be withdrawn at any time at the discretion of the Investigator or sponsor for safety or behavioral reasons, or the inability of the subject to comply with the protocol required schedule of study visits or procedures at a given study site.

If a subject does not return for a scheduled visit, every effort should be made to contact the subject. For withdrawn subjects, the Investigator should inquire about the reason for withdrawal, request the subject return all unused investigational product, request the subject to return for an early termination visit, and follow up with the subject regarding any unresolved adverse events (AEs).

If the subject withdraws from the trial, and also withdraws consent for disclosure of future information, no further evaluations should be performed, and no additional data should be collected. The sponsor may retain and continue to use any data collected before such withdrawal of consent.

Subjects who discontinue treatment with blinded investigational product for reasons other than withdrawn consent should attend the clinic for a visit where all early termination procedures are performed followed by a post-treatment telephone call 14 days after the last dose of blinded investigational product. Thereafter, subjects will be followed by telephone contacts according to the study visit schedule until the end of the trial (Week 26), but will not have other procedures performed that are outlined in the study schedule of activities. The purpose of the telephone contacts, as well as the 14-day post-treatment telephone call, is to collect information about subjects’ health status (ie, evaluate if the subject experienced any SAEs or events eligible for adjudication [see [Section 7.6](#)]).

If a subject indicates his or her intention to stop active participation in the trial (ie, chooses to no longer attend visits at the investigational site, take blinded investigational product, and have other study-related procedures conducted at the investigational site), or if the Investigator has recommended stopping the investigational product, the Investigator must

clarify with the subject if he/she is willing to continue in the study with contact at intervals to provide a brief and focused update on health status (eg, SAEs and events eligible for adjudication [see [Section 7.6](#)]). It will be important for the subject to understand the importance of complete collection of information, and also the limited requirements for continuing to provide this information (ie, a brief telephone contact, occurring at the time of the originally planned study visits). Thus, subjects may discontinue investigational product and continue in the study with clinic visits or allow continued site contacts without clinic visits, or they may indicate that they do not wish to have further contact with the site.

Procedures will be put in place and described in the Informed Consent Document to ensure that if a subject loses contact with the trial site, alternative measures will be utilized for the collection of information on clinical cardiovascular events. This may include contacting family members and health care providers and, when applicable, using subject location services. Sites should make at least three attempts for a telephone contact. If the three attempts of telephone contact are unsuccessful, sites should make at least two attempts to reach the subject via certified letter. All attempts to contact a subject and information received during contact attempts must be documented in the subject's medical record. In any circumstance, every effort should be made to document subject outcome, if possible. The Investigator should inquire about the reason for withdrawal, requests the subject to return all unused investigational product(s), requests the subject to return for a final visit, if applicable, and follow up with the subject regarding any unresolved AEs.

Subjects who are discontinued from investigational product but agree to continue to participate in the trial by providing follow-up information can have medical and diabetes management by their managing physician or Investigator, as appropriate. These subjects may initiate any other therapy as needed (previously prohibited medications may be used). After discontinuation of investigational product, Pfizer or its designee will continue to reimburse/supply (as specified in [Section 5.6.1](#)), glimepiride (for those rescued) until Week 26. The Investigator should ensure that the subject has enough open-label rescue medication until the next scheduled in clinic visit (if applicable). Procurement of any other AHAs is the responsibility of the subject.

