Metformin + another single allowable AHA*	6.5%–9.5% (48-80 mmol/mol), inclusive	Discontinue the non-metformin AHA. Titrate metformin dose to ≥ 1500 mg/day** (if needed). The dose stable period for metformin monotherapy must be ≥ 8 weeks.

HbA1c = Glycosylated hemoglobin; AHA = Anti-hyperglycemic agent; S1 = Initial screening visit; S2/S3 = Combined Screening Visits 2 and 3.

*allowable AHA agents are sulfonylurea, DPP-4 inhibitor, meglitinide, or alpha-glucosidase inhibitor.

** metformin can be uptitrated over a period of up to 4 weeks.

The trial is designed with two phases:

Met=Metformin

- 1. Screening phase including discontinuation of background diabetes therapy other than metformin (if applicable) and a single-blind placebo run-in period (Visits S1 up to V4)** - the length of this standardization period will vary depending on the diabetes therapy of subjects at S1 (metformin monotherapy ≥ 1500 mg/day for ≥ 8 weeks or for < 8 weeks, metformin monotherapy < 1500 mg/day or metformin + another single allowable AHA) as shown in [Table 1](#).
- 2. Treatment Phase: Randomized, double-blind, placebo-controlled treatment period (Visits V4 through V8)** - a 26-week treatment period for assessment of primary efficacy and safety endpoints along with secondary efficacy endpoints. At entry into the double-blind treatment phase, subjects will be randomized to ertugliflozin 5 mg, ertugliflozin 15 mg, or placebo, while maintaining metformin at a stable dose (≥ 1500 mg/day). Glycemic rescue therapy with open-label glimepiride will be initiated in subjects with glucose values exceeding protocol-specified values as provided in [Section 5.6](#). Dosing and titration of open-label glimepiride rescue therapy will be at the Investigator's discretion. After initiation of rescue therapy, background metformin (same dose and regimen) and blinded investigational product will continue to be taken by the subject. Each randomized subject should have a follow-up phone call 14 days after the last dose of investigational product to assess for AE (adverse event)s, SAE (serious adverse event)s and collect information on clinical events per [Section 7.6](#), if applicable.

The trial is designed to evaluate the efficacy, safety and tolerability of the 5 mg and 15 mg oral doses of ertugliflozin on glycemic control, body weight, and blood pressure following a 26-week dosing period in Asian adult subjects with T2DM and inadequate glycemic control on metformin monotherapy.

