Metformin monotherapy, < 1500 mg/day	7.5%–11.0% (58-97 mmol/mol), inclusive	Titrate metformin dose to ≥ 1500 mg/day.** The dose stable period must be ≥ 8 weeks.
Metformin + another single allowable AHA*	6.5%–9.5% (48-80 mmol/mol), inclusive	Discontinue the non-metformin AHA. Titrate metformin dose to ≥ 1500 mg/day** (if needed). The dose stable period for metformin monotherapy must be ≥ 8 weeks.

HbA1c = Glycosylated hemoglobin; AHA = Anti-hyperglycemic agent; S1 = Initial screening visit;

[figure not shown]
S2/S3 = Combined Screening Visits 2 and 3.

*allowable AHA agents are sulfonylurea, DPP-4 inhibitor, meglitinide, or alpha-glucosidase inhibitor.

** metformin can be uptitrated over a period of up to 4 weeks.

Figure 1 summarizes the overall trial scheme.

Figure 1. Trial Scheme

Met=Metformin

The trial is designed with two phases:

- 1. Screening phase including discontinuation of background diabetes therapy other than metformin (if applicable) and a single-blind placebo run-in period (Visits S1 up to V4)** - the length of this standardization period will vary depending on the diabetes therapy of subjects at S1 (metformin monotherapy ≥ 1500 mg/day for ≥ 8 weeks or for < 8 weeks, metformin monotherapy < 1500 mg/day or metformin + another single allowable AHA) as shown in Table 3.
- 2. Treatment Phase: Randomized, double-blind, placebo-controlled treatment period (Visits V4 through V8)** - a 26-week treatment period for assessment of primary efficacy and safety endpoints along with secondary efficacy endpoints. At entry into double-blind treatment phase, subjects will be randomized to ertugliflozin 5 mg, ertugliflozin 15 mg, or placebo, while maintaining metformin at a stable dose (the metformin dose at which the subject entered the metformin dose-stable run-in period). Glycemic rescue therapy with open-label glimepiride will be initiated in subjects with glucose values exceeding protocol-specified values as provided in [Section 5.6](#). Dosing and titration of open-label glimepiride rescue therapy will be at the Investigator's discretion. After initiation of rescue therapy, background metformin (same dose and regimen) and blinded investigational product will continue to be taken by the subject. Each randomized subject should have a follow-up phone call 14 days after the last dose of investigational product to assess for AEs, SAEs and collect information on clinical events per [Section 7.6](#), if applicable.

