6.4. Follow-up Phone Call

Each randomized subject should have a follow-up phone call 14 days after the last dose of investigational product to assess for AEs, SAEs and collect information on clinical events per [Section 7.6](#), if applicable. The phone call should be completed within a ± 3 day window.

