Note: A consistent value is defined as a repeat measurement performed within 7 days of notification from the central laboratory. If the eGFR or serum creatinine value continues to meet discontinuation criterion but demonstrates improvement relative to the prior result, an additional repeat may be performed (within 7 days). If this repeat continues to meet the discontinuation criteria, the subject must be discontinued from investigational product. See [Section 6.6.1.1](#) for guidance on following subjects who discontinue due to decreased renal function or renal-related adverse events.

5. Requirement for one of the prohibited medications listed in [Section 5](#). Subjects temporarily placed on a prohibited medication by a non-study physician that has been stopped and which is not clinically necessary may continue in the study.
6. For subjects who are on glycemic rescue medication, and found to be hypersensitive to or intolerant to glimepiride or if such a subject develops any condition for which glimepiride is contraindicated in accordance with the local drug label of the country where the subject is participating.

7. Pregnancy.

Note: A positive urine pregnancy test requires immediate interruption of investigational product until serum β -hCG can be performed and found to be negative. Subject must be permanently discontinued, and pregnancy should be reported and followed per [Section 8.3](#) if pregnancy is confirmed by a positive serum pregnancy test.

8. Any medical condition or personal circumstance which, in the opinion of the Investigator, exposes the subject to risk by continuing in the trial or does not allow the subject to adhere to the requirements of the protocol.
9. Subjects undergoing bariatric surgery.
10. The Investigator or subject are unblinded to randomized assignment (eg, unblinding information obtained through IVRS or inadvertently obtained).
11. Subject's decision: Subject no longer agrees to actively participate in the study (ie, take blinded investigational product or other required concomitant study medication, attend study visits, or otherwise comply with study procedures) but agrees to be contacted at times of regular study visits to collect health status (ie, SAEs and adjudicated events).

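### Section 6.6 confines the 14-day post-treatment call for subjects who stop investigational product to SAEs and adjudicable events, while Section 6.4, the Schedule of Activities and Section 8.1 call for all AEs

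*Combined protocol and SAP*

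**What the plan says.** Section 6.6 deals with subjects who discontinue blinded investigational product for reasons other than withdrawn consent. They attend an early termination visit, are telephoned 14 days after the last dose, and are then telephoned on the visit schedule until Week 26. One purpose statement covers both kinds of call: "The purpose of the telephone contacts, as well as the 14-day post-treatment telephone call, is to collect information about" health status. That term is then defined, after *ie*, as finding out whether to "evaluate if the subject experienced any SAEs or events eligible for adjudication" applies; non-serious AEs that are not adjudicable do not appear.

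Other parts of the protocol describe the same call, or its time window, more broadly:

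- Section 6.4, for each randomized subject: "to assess for AEs, SAEs and collect information on clinical events per" Section 7.6.
- Section 3: "Each randomized subject should have a follow-up phone call 14 days after the last dose of investigational product to assess for AEs, SAEs", and Section 7.6 events.
- Protocol summary, treatment phase: "to assess for AE (adverse event)s, SAE (serious adverse event)s and collect information on clinical events per" Section 7.6.
- Schedule of Activities: the adverse event monitoring row is marked at the 2-week call, and its footnote v asks for AEs, SAEs and potential adjudicable events.
- Section 8.1: all AEs are to be recorded from consent through 14 days after treatment stops.

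The Schedule's own footnote to the 2-week call mentions only SAEs and Section 7.6 events, for every randomized subject.

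**The concern.** Subjects who discontinue are randomized subjects, so Sections 6.4 and 6.6 both govern their 14-day call and give it different content. The introduction to the Schedule sends the reader to the study procedures and assessments sections for detail, and the procedures section contains both versions. A site could reasonably treat Section 6.6 as the specific rule for discontinuers and ask only about SAEs and adjudicable events.

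The call falls at the end of the window in which Section 8.1 wants every AE recorded. Safety and tolerability is a primary objective (Section 2.1), and the Tier-1 events in Section 9.3 include urinary tract infection, genital mycotic infection, symptomatic hypoglycemia and hypovolemia, many of which would be non-serious. What is at stake is uniform inquiry about non-serious AEs in the last days of the recording window. SAEs and adjudicable events are captured under every version.

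**Working it through.** **Text comparison.** The question is whether the passages can be read together.

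| Place | Who | Non-serious AEs at the 14-day call? |
|---|---|---|
| Section 6.6 | Subjects who stop product, consent not withdrawn | Left out; content defined with *ie* |
| Section 6.4 | Each randomized subject | Yes |
| Summary and Section 3 | Each randomized subject | Yes |
| Schedule, AE row and footnote v | All | Yes |
| Section 8.1 | All, through 14 days after treatment stops | Yes (recording duty) |
| Schedule, call footnote | Each randomized subject | Not mentioned |

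1. *Is the Schedule mark really at the call?* The AE row has nine marks against ten columns: S2, S3, V4, V5, V6, V7, V8, the 2-week call and the Rescue Visit. Only S1 is blank, so the call is marked.
2. *Do neighbouring passages soften Section 6.6?* Further on, Section 6.6 asks whether the subject is willing "to provide a brief and focused update on health status (eg, SAEs and events eligible for adjudication". There *eg* gives examples, but the sentence concerns contact at intervals, not the 14-day call. Section 6.6.1 item 11 describes a subject who "agrees to be contacted at times of regular study visits to collect health status (ie, SAEs and adjudicated events"; that is restrictive, but tied to regular visit times. Neither changes the statement that names the 14-day call.
3. *Does follow-up of unresolved AEs close the gap?* No. It covers AEs already known, not new ones that begin after the early termination visit.
4. *Is the restriction a problem for the later calls?* Not after the 14-day call, when the Section 8.1 window has normally closed. The Schedule's early termination footnote already lists the 2-week call separately from the later SAE and Section 7.6 contacts.

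**Size.** There is no figure in the plan to reproduce. Two rough bounds can be formed.

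- *Subjects.* Inputs: about 20% premature withdrawal (Sections 3 and 9.1), 495 randomized, 165 per arm. 0.20 × 495 = 99 in total; 0.20 × 165 = 33 per arm. The 20% also counts rescued subjects, who continue product (Section 5.6), and subjects who leave the study. If the assumption holds, fewer than 99 fall under this part of Section 6.6.
- *Days without active inquiry.* With the early termination visit d days after the last dose, the period left in the 14-day window is 14 − d. The documents do not fix d, so these values are assumed:
  - d = 0: 14 − 0 = 14 days
  - d = 1: 14 − 1 = 13 days
  - d = 7: 14 − 7 = 7 days (a timing that Section 6.6.1.1 contemplates for renal discontinuers)
  - d = 14: 14 − 14 = 0 days

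The call has a ±3-day window. A call on day 14 − 3 = 11 would reach only to day 11 even under Section 6.4, so the difference between the two versions would then be 3 days smaller when d is 11 or less. These are limits on the time without active questioning, not counts of lost events.

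**The case against.** The best defence is that Section 6.6 states a purpose and does not say *only*. A site that follows Sections 6.4 and 8.1 also satisfies Section 6.6, so the duties are not strictly incompatible. Footnote v, attached to the AE row, sends the reader to Section 8 for detail, and Section 8 holds the all-AE rule. The *eg* used later in Section 6.6 for a similar update suggests loose drafting. The practical loss is also buffered: AEs are asked about at the early termination visit (Section 6.3.5), unresolved AEs are followed, and the protocol provides for symptoms reported between visits, such as urinary tract symptoms (Section 7.4.7.1) and suspected genital fungal infection (Section 7.4.7.2). Section 9.3 gives no window for treatment-emergent AEs, so an effect on the AE tables cannot be demonstrated.

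Most of this stands as a limit on importance. It also shows that all-AE inquiry is very probably what was intended. It does not remove the conflict: Section 6.6 names the call, defines its content with *ie*, and addresses exactly the subjects in question. The planning figure of 99 is fairly criticised too. It rests on an approximate assumption, does not cap actual discontinuations and mixes several groups, so it is not evidence of impact.

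**Conclusion.** The concern holds, as a minor point. For subjects who stop investigational product, the protocol gives two different contents for the same 14-day call, and Section 6.6 as written is out of line with Sections 3, 6.4 and 8.1, the summary and the Schedule's AE row. The Schedule's call footnote is a secondary mismatch: it omits AEs but does not define the content exclusively, and the same Schedule requires AE assessment at that call.

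The exposure is confined to new, non-serious, non-adjudicable AEs that begin after the early termination visit, are not volunteered, and occur at sites that follow Section 6.6 literally. The number of such AEs, any difference between arms and any effect on the Tier-1 comparisons are not shown, because the documents give neither an event rate for this period nor the timing of the early termination visit.

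**What to change.** 1. In Section 6.6, split the purpose statement. State that the 14-day post-treatment call assesses AEs, SAEs and clinical events per Section 7.6, as in Section 6.4. Keep the present SAE and adjudication wording for telephone contacts made after that call.
2. In the Schedule of Activities, add AEs to the footnote on the 2-week follow-up call, so that it agrees with Section 6.4 and footnote v.

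The cost is two wording edits, which can go into the next amendment submitted for IRB/IEC approval under Section 12.1. The call already takes place, so no visit, contact or procedure is added.

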6.6.1. Reasons for Discontinuation from Investigational Product or from the Trial

Reasons for protocol-specified discontinuation from the investigational product or from the trial are listed, but not limited, below. All subjects will be followed until resolution (ie, return to baseline values or diagnosis determined or new stable state established, based upon Investigator and Sponsor [or its delegate] assessment) for any laboratory safety test abnormality resulting in discontinuation from investigational product.

Withdrawal from the Trial

- Subject requests discontinuation from the trial (ie, refuses to continue to be contacted to provide further health information).
- Death.

Discontinuation of Investigational Product

1. Subject meets protocol-specified hyperglycemia criteria as specified below:

Subject has been rescued with glimepiride and is on the maximum labeled or maximum-tolerated dose (if lower than the maximum labeled dose) for at least 4 weeks, and continues to meet glycemic thresholds specified in [Table 4](#) for the relevant time point in the trial, without a reasonable explanation (eg, intercurrent illness or medication omission).

2. Hypoglycemia: Repeated (2 or more episodes since the prior visit) FPG or fingerstick glucose <50 mg/dL (<2.8 mmol/L) with or without symptoms of hypoglycemia or ≤70 mg/dL (≤3.9 mmol/L) with symptoms of hypoglycemia, and without a reasonable explanation (such as increased physical activity or skipped meal) or with a reasonable explanation and likely to reoccur.

Note: For subjects rescued with glimepiride, the protocol-specified discontinuation criteria for hypoglycemia only apply after the subject has interrupted glycemic rescue medication.

3. Abnormal liver function tests meeting discontinuation criteria specified in [Section 8.7](#).

4. Parameters of Renal Function:

- Serum creatinine concentrations consistently ≥1.5 mg/dL (133 µmol/L) in men or ≥1.4 mg/dL (123 µmol/L) in women.

OR

- Subjects with eGFR consistently <45 mL/min/1.73 m² (MDRD formula).

Note: A consistent value is defined as a repeat measurement performed within 7 days of notification from the central laboratory. If the eGFR or serum creatinine value continues to meet discontinuation criterion but demonstrates improvement relative to the prior result, an additional repeat may be performed (within 7 days). If this repeat continues to meet the discontinuation criteria, the subject must be discontinued from investigational product. See [Section 6.6.1.1](#) for guidance on following subjects who discontinue due to decreased renal function or renal-related adverse events.

5. Requirement for one of the prohibited medications listed in [Section 5](#). Subjects temporarily placed on a prohibited medication by a non-study physician that has been stopped and which is not clinically necessary may continue in the study.
6. For subjects who are on glycemic rescue medication, and found to be hypersensitive to or intolerant to glimepiride or if such a subject develops any condition for which glimepiride is contraindicated in accordance with the local drug label of the country where the subject is participating.

7. Pregnancy.

Note: A positive urine pregnancy test requires immediate interruption of investigational product until serum β -hCG can be performed and found to be negative. Subject must be permanently discontinued, and pregnancy should be reported and followed per [Section 8.3](#) if pregnancy is confirmed by a positive serum pregnancy test.

8. Any medical condition or personal circumstance which, in the opinion of the Investigator, exposes the subject to risk by continuing in the trial or does not allow the subject to adhere to the requirements of the protocol.
9. Subjects undergoing bariatric surgery.
10. The Investigator or subject are unblinded to randomized assignment (eg, unblinding information obtained through IVRS or inadvertently obtained).
11. Subject's decision: Subject no longer agrees to actively participate in the study (ie, take blinded investigational product or other required concomitant study medication, attend study visits, or otherwise comply with study procedures) but agrees to be contacted at times of regular study visits to collect health status (ie, SAEs and adjudicated events).

If a subject discontinues investigational product, he/she should complete all Early Termination Visit procedures as described in [Section 6.3.5](#) and listed in [Schedule of Activities](#). Unless the consent to follow the subject is specifically withdrawn, a subject will be contacted via telephone by the Investigator/qualified designee according to the same schedule as if he/she were still taking investigational product and will be asked to return for a visit at Week 26. Such subjects may initiate other AHA therapy as indicated (prohibited medications described in [Section 5.5](#) will not apply to these subjects.)

